##### **6.4.4. Compliance (Diary Review)**

Subject diaries will be reviewed by the Investigator or their designee. Subjects who apply the washout products (All subjects) and test product (Group I, only) more or less frequently than twice a day will be considered to have deviated from the protocol and additional/missed applications will be recorded on the Deviations Log. The total number of product applications and total number of missed product applications will be recorded on the eCRF.

Document Name	Protocol 206827 CCI doc	Document Identifier	Effective Date
Type	Version		
elido controlled	4.0; Most-Recent; Effective; CURRENT	090032d580d98eb9	15-Sep-2017 09:27:15
Reason For Issue	Auto Issue		

#### **6.4.5. Instrumental Measurements Post-Procedure, Post-Treatment (24±4 hours after Facial Peel)**

Measurements to be taken and recorded as per 6.3.10, 24±4 hours after completion of the facial peel procedure.

#### **6.4.6. Image Capture (VISIA) Post-Procedure, Post-Treatment (24±4 hours after Facial Peel)**

Assessments to be taken and recorded as per 6.3.11, 24±4 hours after completion of the facial peel procedure.

#### **6.4.7. Subject Self-Assessment Post-Procedure, Post-Treatment (24±4 hours after Facial Peel)**

Assessments to be taken and recorded as per 6.3.12, 24±4 hours after completion of the facial peel procedure.

#### **6.4.8. Dermatologist Assessment Post-Procedure, Post-Treatment (24±4 hours after Facial Peel)**

Assessments to be taken and recorded as per 6.3.13, 24±4 hours after completion of the facial peel procedure.

#### **6.4.9. Supervised Test Product Application**

Only subjects in Group I will undergo supervised test product application. The Investigator or designee will oversee application of the test product. Product application will be recorded on the eCRF and subject diary. The Investigator or designee involved in this step must not be involved in any assessments in order to protect the blind.

#### **6.4.10. Supervised Sunscreen Application**

All subjects will undergo supervised sunscreen application. The Investigator or designee will oversee application of the SPF 50 sunscreen. Product application will be recorded on the eCRF and subject diary.

### **6.5. Visit 5 – 1 day after Visit 4**

Subjects will be instructed to arrive at the site prior to 9:00 AM to minimize exposure to intense sunlight.

Document Name	Protocol 206827 CCI doc		
Type	Version	Document Identifier	Effective Date
elido controlled	4.0; Most-Recent; Effective; CURRENT	090032d580d98eb9	15-Sep-2017 09:27:15
Reason For Issue	Auto Issue		

### 6.5.1. Current / Concomitant Medication

Any concomitant therapy taken since the last visit and throughout the study will be recorded on the eCRF by the Investigator or designee.

### 6.5.2. Adverse Events

Adverse events will be assessed by the Investigator or designee and recorded on the eCRF, as per the process detailed in Section 7.

As per Section 7.1, the following does not meet the definition of an adverse event: “Any clinically significant abnormal laboratory findings (if applicable) or other abnormal safety assessments which are associated with the underlying disease, unless judged by the investigator to be more severe than expected for the subject’s condition.” Therefore, the Dermatologist (erythema, edema, dryness, and desquamation) and Subject-self assessment (pain, stinging/burning, itching, tightness, redness, and dryness) grades will only be considered adverse events if they are scored as “Severe”, or if the investigator judges them to be more severe than expected in context of the Glycolic Acid treatment procedure.

### 6.5.3. Continued Subject Eligibility

The Investigator or designee will ascertain whether there have been any deviations from the protocol since the last visit, whether the subject has adhered to the lifestyle restrictions since the last visit and whether, in their opinion, the subject is eligible to continue in the study. Subject Continued Subject Eligibility will be recorded on the eCRF.

### 6.5.4. Compliance (Diary Review)

Subject diaries will be reviewed by the Investigator or their designee. Subjects who apply the washout products (All subjects) and test product (Group I, only) more or less frequently than twice a day will be considered to have deviated from the protocol and additional/missed applications will be recorded on the Deviations Log. The total number of product applications and total number of missed product applications will be recorded on the eCRF.

### 6.5.5. Instrumental Measurements Post-Procedure, Post-Treatment (48±4 hours after Facial Peel)

Measurements to be taken and recorded as per 6.3.10, 48±4 hours after completion of the facial peel procedure.

Document Name	Protocol 206827 CCI doc		
Type	Version	Document Identifier	Effective Date
elido controlled	4.0; Most-Recent; Effective; CURRENT	090032d580d98eb9	15-Sep-2017 09:27:15
Reason For Issue	Auto Issue		

### **6.5.6. Subject Self-Assessment Post-Procedure, Post-Treatment (48±4 hours after Facial Peel)**

Assessments to be taken and recorded as per 6.3.12, 48±4 hours after completion of the facial peel procedure.

### **6.5.7. Dermatologist Assessment Post-Procedure, Post-Treatment (48±4 hours after Facial Peel)**

Assessments to be taken and recorded as per 6.3.13, 48±4 hours after completion of the facial peel procedure.

### **6.5.8. Supervised Test Product Application**

Only subjects in Group I will undergo supervised test product application. The Investigator or designee will oversee application of the test product. Product application will be recorded on the eCRF and subject diary. The Investigator or designee involved in this step must not be involved in any assessments in order to protect the blind.

### **6.5.9. Supervised Sunscreen Application**

All subjects will undergo supervised sunscreen application. The Investigator or designee will oversee application of the SPF 50 sunscreen. Product application will be recorded on the eCRF and subject diary.

## **6.6. Visit 6 – 1 day after Visit 5**

Subjects will be instructed to arrive at the site prior to 9:00 AM to minimize exposure to intense sunlight.

### **6.6.1. Current / Concomitant Medication**

Any concomitant therapy taken since the last visit and throughout the study will be recorded on the eCRF by the Investigator or designee.

### **6.6.2. Adverse Events**

Adverse events will be assessed by the Investigator or designee and recorded on the eCRF, as per the process detailed in Section 7.

As per Section 7.1, the following does not meet the definition of an adverse event: “Any clinically significant abnormal laboratory findings (if applicable) or other abnormal safety assessments which are associated with the underlying disease, unless judged by the investigator to be more severe than expected for the subject’s

Document Name	Protocol 206827 CCI doc		
Type	Version	Document Identifier	Effective Date
eldo controlled	4.0; Most-Recent; Effective; CURRENT	090032d580d98eb9	15-Sep-2017 09:27:15
Reason For Issue	Auto Issue		

condition.” Therefore, the Dermatologist (erythema, edema, dryness, and desquamation) and Subject-self assessment (pain, stinging/burning, itching, tightness, redness, and dryness) grades will only be considered adverse events if they are scored as “Severe”, or if the investigator judges them to be more severe than expected in context of the Glycolic Acid treatment procedure.

#### **6.6.3. Continued Subject Eligibility**

The Investigator or designee will ascertain whether there have been any deviations from the protocol since the last visit, whether the subject has adhered to the lifestyle restrictions since the last visit and whether, in their opinion, the subject is eligible to continue in the study. Subject Continued Subject Eligibility will be recorded on the eCRF.

#### **6.6.4. Compliance (Diary Review)**

Subject diaries will be reviewed by the Investigator or their designee. Subjects who apply the washout products (All subjects) and test product (Group I, only) more or less frequently than twice a day will be considered to have deviated from the protocol and additional/missed applications will be recorded on the Deviations Log. The total number of product applications and total number of missed product applications will be recorded on the eCRF.

#### **6.6.5. Instrumental Measurements Post-Procedure, Post-Treatment (72±4 hours after Facial Peel)**

Measurements to be taken and recorded as per 6.3.10, 72±4 hours after completion of the facial peel procedure.

#### **6.6.6. Subject Self-Assessment Post-Procedure, Post-Treatment (72±4 hours after Facial Peel)**

Assessments to be taken and recorded as per 6.3.12, 72±4 hours after completion of the facial peel procedure.

#### **6.6.7. Dermatologist Assessment Post-Procedure, Post-Treatment (72±4 hours after Facial Peel)**

Assessments to be taken and recorded as per 6.3.13, 72±4 hours after completion of the facial peel procedure.

#### **6.6.8. Supervised Test Product Application**

Only subjects in Group I will undergo supervised test product application. The Investigator or designee will oversee application of the test product. Product

Document Name	Protocol 206827 CCI doc		
Type	Version	Document Identifier	Effective Date
elido controlled	4.0; Most-Recent; Effective; CURRENT	090032d580d98eb9	15-Sep-2017 09:27:15
Reason For Issue	Auto Issue		

application will be recorded on the eCRF and subject diary. The Investigator or designee involved in this step must not be involved in any assessments in order to protect the blind.

### **6.6.9. Supervised Sunscreen Application**

All subjects will undergo supervised sunscreen application. The Investigator or designee will oversee application of the SPF 50 sunscreen. Product application will be recorded on the eCRF and subject diary.

## **6.7. Visit 7 – 4 days after Visit 6**

Subjects will be instructed to arrive at the site prior to 9:00 AM to minimize exposure to intense sunlight.

### **6.7.1. Current / Concomitant Medication**

Any concomitant therapy taken since the last visit and throughout the study will be recorded on the eCRF by the Investigator or designee.

### **6.7.2. Adverse Events**

Adverse events will be assessed by the Investigator or designee and recorded on the eCRF, as per the process detailed in Section 7.

As per Section 7.1, the following does not meet the definition of an adverse event: “Any clinically significant abnormal laboratory findings (if applicable) or other abnormal safety assessments which are associated with the underlying disease, unless judged by the investigator to be more severe than expected for the subject’s condition.” Therefore, the Dermatologist (erythema, edema, dryness, and desquamation) and Subject-self assessment (pain, stinging/burning, itching, tightness, redness, and dryness) grades will only be considered adverse events if they are scored as “Severe”, or if the investigator judges them to be more severe than expected in context of the Glycolic Acid treatment procedure.

### **6.7.3. Continued Subject Eligibility**

The Investigator or designee will ascertain whether there have been any deviations from the protocol since the last visit, whether the subject has adhered to the lifestyle restrictions since the last visit and whether, in their opinion, the subject is eligible to continue in the study. Subject Continued Subject Eligibility will be recorded on the eCRF.

Document Name	Protocol 206827 CCI doc		
Type	Version	Document Identifier	Effective Date
eldo controlled	4.0; Most-Recent; Effective; CURRENT	090032d580d98eb9	15-Sep-2017 09:27:15
Reason For Issue	Auto Issue		

#### **6.7.4. Compliance (Diary Review)**

Subject diaries will be reviewed by the Investigator or their designee. Subjects who apply the washout products (All subjects) and test product (Group I, only) more or less frequently than twice a day will be considered to have deviated from the protocol and additional/missed applications will be recorded on the Deviations Log. The total number of product applications and total number of missed product applications will be recorded on the eCRF.

#### **6.7.5. Instrumental Measurements Post-Procedure, Post-Treatment (168±4 hours after Facial Peel)**

Measurements to be taken and recorded as per 6.3.10, 168±4 hours after completion of the facial peel procedure.

#### **6.7.6. Subject Self-Assessment Post-Procedure, Post-Treatment (168±4 hours after Facial Peel)**

Assessments to be taken and recorded as per 6.3.12, 168±4 hours after completion of the facial peel procedure.

#### **6.7.7. Dermatologist Assessment Post-Procedure, Post-Treatment (168±4 hours after Facial Peel)**

Assessments to be taken and recorded as per 6.3.13, 168±4 hours after completion of the facial peel procedure.

#### **6.7.8. Supervised Test Product Application**

Only subjects in Group I will undergo supervised test product application. The Investigator or designee will oversee application of the test product. Product application will be recorded on the eCRF and subject diary. The Investigator or designee involved in this step must not be involved in any assessments in order to protect the blind.

#### **6.7.9. Supervised Sunscreen Application**

All subjects will undergo supervised sunscreen application. The Investigator or designee will oversee application of the SPF 50 sunscreen. Product application will be recorded on the eCRF and subject diary.

### **6.8. Visit 8 – 7 days after Visit 7**

Subjects will be instructed to arrive at the site prior to 9:00 AM to minimize exposure to intense sunlight.

Document Name	Protocol 206827 CCI doc		
Type	Version	Document Identifier	Effective Date
eldo controlled	4.0; Most-Recent; Effective; CURRENT	090032d580d98eb9	15-Sep-2017 09:27:15
Reason For Issue	Auto Issue		

### 6.8.1. Current / Concomitant Medication

Any concomitant therapy taken since the last visit and throughout the study will be recorded on the eCRF by the Investigator or designee.

### 6.8.2. Adverse Events

Adverse events will be assessed by the Investigator or designee and recorded on the eCRF, as per the process detailed in Section 7.

As per Section 7.1, the following does not meet the definition of an adverse event: “Any clinically significant abnormal laboratory findings (if applicable) or other abnormal safety assessments which are associated with the underlying disease, unless judged by the investigator to be more severe than expected for the subject’s condition.” Therefore, the Dermatologist (erythema, edema, dryness, and desquamation) and Subject-self assessment (pain, stinging/burning, itching, tightness, redness, and dryness) grades will only be considered adverse events if they are scored as “Severe”, or if the investigator judges them to be more severe than expected in context of the Glycolic Acid treatment procedure.

### 6.8.3. Continued Subject Eligibility

The Investigator or designee will ascertain whether there have been any deviations from the protocol since the last visit, whether the subject has adhered to the lifestyle restrictions since the last visit and whether, in their opinion, the subject is eligible to continue in the study. Subject Continued Subject Eligibility will be recorded on the eCRF.

### 6.8.4. Compliance (Diary Review)

Subject diaries will be reviewed by the Investigator or their designee. Subjects who apply the washout products (All subjects) and test product (Group I, only) more or less frequently than twice a day will be considered to have deviated from the protocol and additional/missed applications will be recorded on the Deviations Log. The total number of product applications and total number of missed product applications will be recorded on the eCRF.

### 6.8.5. Instrumental Measurements Post-Procedure, Post-Treatment (336±4 hours after Facial Peel)

Measurements to be taken and recorded as per 6.3.10, 336±4 hours after completion of the facial peel procedure.

Document Name	Protocol 206827 CCI doc		
Type	Version	Document Identifier	Effective Date
elido controlled	4.0; Most-Recent; Effective; CURRENT	090032d580d98eb9	15-Sep-2017 09:27:15
Reason For Issue	Auto Issue		

### **6.8.6. Image Capture (VISIA) Post-Procedure, Post-Treatment (336±4 hours after Facial Peel)**

Assessments to be taken and recorded as per 6.3.11, 336±4 hours after completion of the facial peel procedure.

### **6.8.7. Subject Self-Assessment Post-Procedure, Post-Treatment (336±4 hours after Facial Peel)**

Assessments to be taken and recorded as per 6.3.12, 336±4 hours after completion of the facial peel procedure.

### **6.8.8. Subject Global Self-Assessment**

Test subjects will rate the level of satisfaction with the post-procedure skin care regimen to which they were randomized using scale below. These data will be recorded on the eCRF.

Score	Description
0	Very Satisfied
1	Satisfied
2	Poorly Satisfied
3	Not at all Satisfied

### **6.8.9. Dermatologist Assesment Post-Procedure, Post-Treatment (336±4 hours after Facial Peel)**

Assessments to be taken and recorded as per 6.3.13, 336±4 hours after completion of the facial peel procedure.

### **6.8.10. Dermatologist Global Assessment**

The Dermatologist will assess the local tolerance of the post-procedure skin care regimen in context of the expected effects of the procedure for each subject using the scale below and document the score on the eCRF. To make this assessment, the Dermatologist will draw on the total set of clinical and subject self-assessment data for each subject. The Dermatologist must be unaware of whether a subject was randomized to test product to protect the blind.

Document Name	Protocol 206827 CCI doc		
Type	Version	Document Identifier	Effective Date
elido controlled	4.0; Most-Recent; Effective; CURRENT	090032d580d98eb9	15-Sep-2017 09:27:15
Reason For Issue	Auto Issue		

Rating	Description
0 - Product Regimen was Well Tolerated	No clinically significant worsening of the expected signs/symptoms of the procedure. No new signs/symptoms manifest during product use.
1 - Product Regimen was Not Well Tolerated	Clear, clinically relevant worsening of the severity or frequency of expected signs/symptoms of the procedure and/or any occurrence of new, unexpected signs/symptoms during product use.

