Supervised Test-Product Application 				X	X	X	X	
Supervised Sunscreen Application 				X	X	X	X	
Products and Test Diary Return								X
Discharge from Study								X

 GlaxoSmithKline	Document Name	Protocol 206827 CCI doc		
	Type	Version	Document Identifier	Effective Date
	elido controlled	4.0; Most-Recent; Effective; CURRENT	090032d580d98eb9	15-Sep-2017 09:27:15
	Reason For Issue	Auto Issue		

1. For Visits 3-8, subjects will be instructed to cleanse their face at home using the cleanser provided and must not use any other product on their face, including the test product (Group I only) and sunscreen. Subjects will be instructed to bring the dispensed cleanser, sunscreen and test product (Group I only) with them to all visits. Subjects will be invited to the site in the morning (prior to 9 am) to avoid exposure to strong sunlight.
2. The Investigator or designee will review the diary to monitor and encourage compliance. Additional or missed product applications will be recorded as deviations. The Evaluator must be blind to diary review.
3. Exclusion Criteria 9 will not be included for this assessment. Exclusion criteria 9 is evaluated based on the results from the sensitivity test.
4. To include a review of the inclusion/exclusion criteria specified in Appendix 4. Subjects must be considered compliant with these inclusion/exclusion criteria in order to remain eligible for the study.
5. Peel regimen (70% Glycolic Acid facial peel solution, Bicarbonate Neutralizing Solution and Sunmax Sensitive SPF 50) to be applied to the volar forearm of each subject by a qualified dermatologist.
6. Assessments to be taken 45±15 minutes after completion of the study material sensitivity test.
7. Assessments to be taken 24±4 hours after completion of the study material sensitivity test.
8. Assessments to be taken 7 days after completion of the study material sensitivity test.
9. 70% Glycolic Acid facial peel to be administered by a qualified dermatologist who must be blind to randomization. The Glycolic Acid treatment and neutralizing solution will be sourced commercially by the study site.
10. Assessments to be taken 60±15 minutes after completion of the facial peel procedure.
11. Only subjects randomised to Group I will be dispensed test product. Subjects in Group I and II will be dispensed different test diaries to reflect the difference in treatment allocation. The washout diary will be returned at the same time as test diary dispensing.

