## 2. OBJECTIVE(S) AND ENDPOINT(S)

Objective(s)	Endpoint(s)
Primary	
Assessment of the local tolerance of the test product in subjects who have undergone a 70% Glycolic Acid facial peel	Evaluator (Dermatologist) global assessment of tolerance
Secondary	
Assessment of skin recovery (change from baseline) over a period of 14 days in subjects who have undergone a 70% Glycolic Acid facial peel	Combined (sum of) Evaluator (Dermatologist) scores for signs/symptoms of erythema, edema, desquamation and dryness  Individual Evaluator (Dermatologist) scores for erythema, edema, desquamation and dryness  Combined (sum of) subject self-assessment scores for redness, pain, stinging/burning, itching, tightness and dryness  Individual subject self-assessment scores for redness, pain, stinging/burning, itching, tightness and dryness  Instrumental measurement of barrier function (Tewameter) and moisturisation (Corneometer)  Subject global self-assessment
Assessment of skin recovery (change from baseline) between treatment groups.	All assessments and measurements listed above

Document Name	Protocol 206827 CCI doc	Document Identifier	Effective Date
Type	Version		
eldo controlled	4.0; Most-Recent; Effective; CURRENT	090032d580d98eb9	15-Sep-2017 09:27:15

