#### **Visit 8 / Day 22 (7 Days after Visit 7)**

The following assessments will be conducted in the order written:

1. Current / Concomitant Medication
2. Adverse Events
3. Continued Subject Eligibility
4. Compliance (Diary review)
5. Instrumental Measurements Post-Procedure, Post-Treatment\*
6. Image capture (VISIA) Post-Procedure, Post-Treatment\*
7. Subject Self-Assessment Post-Procedure, Post-Treatment\*
8. Subject Global Self-Assessment
9. Dermatologist Assessment Post-Procedure, Post-Treatment\*
10. Dermatologist Global Assessment of Tolerance
11. Products and Test Diary Return
12. Discharge from Study

\* Assessments to be taken 336±4 hours after completion of the facial peel procedure

Document Name	Protocol 206827 CCI doc		
Type	Version	Document Identifier	Effective Date
elido controlled	4.0; Most-Recent; Effective; CURRENT	090032d580d98eb9	15-Sep-2017 09:27:15
Reason For Issue	Auto Issue		

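### The evaluator-blind primary rating is open to two unprotected influences: the unblinded subject's satisfaction score, and a third product that only Group I brings to visits

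*Protocol*

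**What the plan says.** Section 2 of the protocol names one primary endpoint, the "Evaluator (Dermatologist) global assessment of tolerance". Section 6.8.10 makes it a two-category rating at Visit 8, with both categories defined by signs and symptoms. For this rating "the Dermatologist will draw on the total set of clinical and subject self-assessment data for each subject"; no item is excluded. The same paragraph requires the Dermatologist not to know whether the subject was randomised to test product. Section 9.2.3 declares success if more than half of the test product group is rated favourably. Section 9.3.2 allows, but does not require, a comparison between groups.

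Section 6.8.8, titled Subject Global Self-Assessment, reads: "Test subjects will rate the level of satisfaction with the post-procedure skin care regimen to which they were randomized". Of the Visit 8 list the protocol says: "The following assessments will be conducted in the order written". In that list "8. Subject Global Self-Assessment" comes first, the Dermatologist sign assessment is step 9 and the Dermatologist global rating is step 10.

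Group II receives no treatment and no vehicle (section 3.4), so subjects know their group. Footnote 1 to the Schedule of Events adds: "Subjects will be instructed to bring the dispensed cleanser, sunscreen and test product (Group I only) with them to all visits".

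**The concern.** A blind rating should rest on information that carries neither the allocation nor the opinion of someone who knows it. Here the rater is given an open-ended set of subject-reported data. One item in that set, read plainly, is satisfaction with the allocated regimen, which is not a sign or symptom and has no place in either category of the rating scale. A rater who sees it may absorb the unblinded subject's view of the product without ever learning the group. The pack route is simpler: from Visit 4 on, a Group I subject arrives with three products and a Group II subject with two.

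At stake are the credibility of the evaluator-blind label on the primary endpoint and the fairness of any comparison of tolerance between groups.

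**Working it through.** The protocol gives no figure for this point, so the main check is to set the sections side by side.

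**Route 1, satisfaction score**
- Input set: all clinical and subject self-assessment data, with no exclusion (6.8.10).
- Item title: Subject Global Self-Assessment (6.8.8).
- Timing: step 8, before the rating at step 10 (Visit 8 lists in the synopsis and section 3.1; the same order in section 6.8). The score exists when the rating is made.
- No section withholds it from the rater.

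**Route 2, carried products**
- Both groups bring cleanser and sunscreen; Group I also brings test product (footnote 1). Test product is dispensed at Visit 3 after the baseline assessments, so Group I brings it to Visits 4 to 8.
- Opaque over-wrapping hides the brand but not the number of packs, and only the test product label carries a code letter (5.9).
- At Visits 4 to 7 supervised application follows the assessments. At Visit 8 product return is step 11, after the primary rating. No section says where the packs are kept before then.

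**Existing safeguards**
- The evaluator is blind to diary review (footnote 2), to test product application (footnote 12), and to allocation and diaries generally (5.8.2).
- Staff who dispense test product or supervise its application do no assessments (6.3.19, 6.3.20, 6.4.9).
- None of these covers the satisfaction score, the sight of packs, or remarks by the subject.

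**What a shift could do to the success verdict**

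Inputs: 40 expected completers per group (9.1) and success if more than 50% are favourable (9.2.3), so at least 21 of 40 are needed. The true favourable rate p is an assumption, because the protocol gives none. With X ~ Binomial(40, p), P(success) = P(X ≥ 21):

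| p | P(success) |
|---|---|
| 45% | 0.21 |
| 50% | 0.44 |
| 55% | 0.68 |
| 60% | 0.87 |
| 70% | 0.994 |
| 80% | 1.000 (rounded) |

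A shift of 5 points is 0.05 × 40 = 2 subjects; 10 points is 4 subjects. From a true rate of 50%, these shifts move P(success) from 0.44 to 0.68 and 0.87. From 70%, a 10-point shift moves it only from 0.994 to about 1.

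**What a shift could do to the comparison**

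The difference in proportions moves one for one with a shift in either group. If ratings moved 5 points up in Group I and 5 points down in Group II, the difference would move 5 + 5 = 10 points, whatever the underlying rate (provided neither group reaches 0% or 100%).

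**How far satisfaction points to the arm (illustration, assumed rates, equal groups)**
- If 85% of Group I and 50% of Group II are satisfied: P(Group I given satisfied) = 0.85/(0.85 + 0.50) = 0.63; P(Group II given dissatisfied) = 0.50/(0.50 + 0.15) = 0.77.
- If 95% and 70%: 0.95/(0.95 + 0.70) = 0.58 and 0.30/(0.30 + 0.05) = 0.86.

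For a satisfied subject the score says little about the arm. The firmer mechanism is the subject's opinion entering the rating, not the rater deducing the group.

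**The case against.** The best case for the plan has four parts.

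- **The satisfaction item may lie outside the set.** The protocol lists Subject Self-Assessment (six symptom scores) and Subject Global Self-Assessment as separate items, and section 6.1.11 uses the self-assessment term for symptom scores only. Both rating categories concern signs and symptoms. This stands in part: 6.8.10 does not name the satisfaction score, and its inclusion is a plain reading rather than an explicit instruction. But the wording is unrestricted and the item's title fits it, so a rater could use it in good faith.
- **Blinding is required in general terms.** Sections 5.8.2 and 6.8.10 state the requirement, and pack handling can be left to site procedure. The requirement is clear, but it is a goal without a step for these two routes, while footnote 1 itself creates the visible difference. The protocol does not say that packs are in view during assessments, only that they are brought.
- **The verdict is single-arm and the comparison optional.** This stands, and it limits the consequence.
- **The symptom scores also come from unblinded subjects.** This stands too. It follows from a no-treatment control and cannot be removed by wording; the scale needs symptom data. It is no reason to add a satisfaction score.

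A reader might also infer that the rater sees the case report form pages on dispensing and application, because "Product application will be recorded on the eCRF and subject diary" and the rating is documented in the same system. The documents do not support this. They say where the rating is recorded, not that the rater reads those pages, and footnotes 2 and 12 and section 5.8.2 forbid that knowledge.

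**Conclusion.** The point holds as a correctable gap in the blinding of the primary endpoint. Two routes are unprotected: the satisfaction score, on a plain reading of 6.8.10, and the third product that Group I alone brings to Visits 4 to 8. The existing safeguards are real but close neither.

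The size of any bias cannot be derived from the protocol. It would fall mainly on the group proportions and the optional between-group comparison. The more-than-50% verdict would be affected only if the true favourable rate were near 50%; the figures assume 40 evaluable subjects in Group I and the stated range of true rates.

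A reader might go further and conclude that the arm is known to the rater with near certainty, that the primary endpoint is in effect an open-label satisfaction result, or that the success decision is unsafe. None of these follows. The protocol does not place packs before the evaluator, the satisfaction score is at most one input among many, and at high tolerance rates the verdict is insensitive to shifts of 5 to 10 points.

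**What to change.** - **Section 6.8.10:** state that the rating uses the Dermatologist sign scores, the six subject symptom scores, the VISIA images where taken, and any recorded new or unexpected signs or symptoms without allocation details. State that the Subject Global Self-Assessment is not shown to the rater. The images must stay because section 6.1.1 says they serve this rating, and new signs or symptoms must stay because the unfavourable category depends on them.
- **Visit 8 lists (synopsis and section 3.1) and section 6.8:** place the Subject Global Self-Assessment after both the Dermatologist sign assessment and the Dermatologist Global Assessment. Moving the global rating ahead of step 8 alone would put it before the Visit 8 sign scores that it needs.
- **Footnote 1 to the Schedule of Events:** have the existing unblinded designee take in all products on arrival, before the evaluator sees the subject, and tell subjects not to mention their products to the evaluator.

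The cost is protocol wording, a reordered Visit 8 list and slight extra handling at the site. It needs no new staff, visit or data, and the rater loses no information on signs or symptoms.
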